**7.13.6. Prohibited medication**

Prohibited medication will be identified on a case-by-case basis by a medical review of the concomitant medication. For the definition of response and time to event variables as described above the first administration of prohibited medication will be relevant. If the day of any prohibited medication is missing, it will be imputed by the first of the month. If day and month are missing, it will be imputed by 1-Jan of the corresponding year.

Subjects in need of systemic corticosteroid therapy other than for prophylaxis and treatment of IRR for more than 7 days may continue being treated with MOR202 but will be excluded from the Per Protocol Analysis Set and the Immunological Analysis Set (IAS). These subjects will be selected on the basis of concomitant medication listing as described above. The ATC level 3 'CORTICOSTEROIDS FOR SYSTEMIC USE, PLAIN' will be selected for individuating patients in systemic use of corticosteroids. Out of these patients, only those who was on therapy for more than 7 days will be excluded from the PPS and IAS.

---

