## STATISTICAL ANALYSIS PLAN

MorphoSys AG  
MOR202C103

- Time to First Immunological Response (in months) prior to start of prohibited treatment (see definition in section 7.13.6) or progression, defined as  
[Date of first documented response of IPR, ICR or sICR (whichever is earlier) – Start date of study drug + 1 day]/30.4375
- Best overall immunological response (BIR) is defined when a subject is classified as having a IPR, ICR, or sIRC at any time during the trial but prior to start of prohibited treatment or progression. Responses for BIR are ordered as IPR < ICR < sICR. If a subject meets the criteria for more than one response category, the subject will be classified in the highest category.
- Time to BIR (in months), defined as  
[Date of BIR – Start date of study drug + 1 day]/30.4375
- Duration of Immunological response (in months), defined as  
[Date of death, PD or start of prohibited treatment (whichever is earlier) – Date of first documented response of IPR, ICR or sICR (whichever is earlier) + 1 day]/30.4375. Subjects with a response but no date of death, PD or start of prohibited treatment at the time of analysis cut-off will be censored at the date of last response assessment. Subjects without a response of IPR, ICR or sICR are assigned a duration time of zero.

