### Proteinuria Response

Proteinuria responses are reflected by the reduction of proteinuria as measured by UPCR. Based on the proteinuria responses, the following response categories are defined by this clinical trial:

- Proteinuria Complete Response (Prot-CR): Reduction of proteinuria to less than 0.5 g/g, serum albumin within the reference range (3.5 – 5.2 g/dL) and stable eGFR (at least 80% of baseline)
- Proteinuria Partial Response (Prot-PR): Reduction by at least 50% of UPCR at a given visit compared to baseline, proteinuria below 3.0 g/g and stable eGFR (at least 80% of baseline), but not meeting Prot-CR

The following variables related to proteinuria responses are defined as follows.

Overall Proteinuria Response (OPR), defined as subjects achieving either Prot-CR or Prot-PR as a response (irrespective of start of prohibited medication or progressive disease prior to the proteinuria response).

Time to First Proteinuria Response (in months) prior to start of prohibited treatment or progression, defined as

[Date of first documented response of Prot-CR or Prot-PR (whichever is earlier) – Start of study drug + 1 day]/30.4375

Best Proteinuria Response (BPR) for a subject is defined when a subject is classified as having a Prot-CR or Prot-PR at any time during the trial but prior to start of prohibited treatment or progression. Responses for BPR are ordered as Prot-PR < Prot-CR. If a subject meets the criteria for more than one response category, the subject will be classified in the highest category.

Time to BPR (in months), defined as

[Date of BPR – Start date of study drug + 1 day]/30.4375

Duration of Proteinuria Response, defined as

[Date of death, PD or start of prohibited treatment (whichever is earlier) – Date of first documented response of Prot-CR or Prot-PR (whichever is earlier) + 1 day]/30.4375. Subjects with a response but no date of death, PD or start of prohibited treatment at the time of analysis

cut-off will be censored at the date of last response assessment. Subjects without a response of Prot-CR or Prot-PR are assigned a duration time of zero.

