**STATISTICAL ANALYSIS PLAN**

 MorphoSys AG  
 MOR202C103

Situation	Time to event variable	Date of event or censoring	Outcome	Censoring Reason
Ongoing and no event until data cut-off	Time to first immunological response, Time to BIR, Time to first proteinuria response, Time to BPR, Time to PD	Date of cut-off	Censored	Ongoing
Discontinued the study with no event	Time to first immunological response, Time to BIR, Time to first proteinuria response, Time to BPR, Time to PD	Date of last response assessment prior to study discontinuation	Censored	Discontinued without event
No baseline assessment for the time to event variable	Time to first immunological response, Time to BIR, Time to first proteinuria response, time to BPR, Time to PD	Date of C1D1	Censored	No baseline assessment
Subject received prohibited treatment before event	Time to first immunological response, Time to BIR, Time to proteinuria response, Time to BPR	Date of last response assessment prior to prohibited treatment	Censored	Start of prohibited treatment
Subject with progressive disease (PD) before event	Time to first immunological response, Time to BIR, Time to first proteinuria response, Time to BPR	Date of documented PD	Censored	Start of PD
No post-baseline assessment for the event variable	Time to first immunological response, Time to BIR, Time to first proteinuria response, time to BPR, Time to PD	Date of C1D1	Censored	No post-baseline assessment

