### 10.1. Analysis of best immunological response rate

The key secondary objective in this trial is to assess the effect of MOR202 on serum anti-PLA2R antibodies in subjects with aMN in terms of best overall immunological response rate (BIRR).

The best overall immunological response (BIR) is defined as achieving any response of IPR, ICR or sICR at any time during the trial but prior to start of prohibited medication or progression based on the definitions in section 7.13.3.

The best overall immunological response rate (BIRR) is defined as the proportion of subjects with a best overall immunological response. The denominator will be the total number of subjects included in the analysis population.

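### Partial start dates for prohibited medication are imputed to the earliest calendar date without using other known data, so an on-study start can be dated before first dose and cancel that subject's best-response and time-to-response results

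*SAP*

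**What the plan says.** SAP 7.13.6 covers both kinds of partial date: "If the day of any prohibited medication is missing, it will be imputed by the first of the month", and "If day and month are missing, it will be imputed by 1-Jan of the corresponding year". It ties the resulting date to the response and time-to-event variables, for which "the first administration of prohibited medication will be relevant". On selection it says "Prohibited medication will be identified on a case-by-case basis by a medical review of the concomitant medication". That review decides which drugs are prohibited, and the section gives it no power to change an imputed date.

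The date is used in three places:

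- **BIR and BPR.** SAP 7.13.3 counts a response only if it occurs "at any time during the trial but prior to start of prohibited treatment or progression". SAP 10.1 repeats this for BIR.
- **BIRR.** SAP 10.1 states: "The denominator will be the total number of subjects included in the analysis population". A subject whose responses are cancelled therefore stays in the denominator as a non-responder.
- **Censoring.** For a subject who took prohibited treatment before the event, the table in SAP 7.13.5 censors time to response at "Date of last response assessment prior to prohibited treatment".

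OPR is different. SAP 7.13.3 counts it "irrespective of start of prohibited medication or progressive disease prior to the proteinuria response". The by-visit response table in SAP 10.1 states no prohibited-medication cut-off of its own.

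**The concern.** Taking the earliest calendar date can contradict what the trial already knows. Suppose a drug was absent from the medication record at several on-treatment visits and was later entered with only a year. The rule can still date its start before the first infusion. Every response the subject had before really starting the drug then fails the condition in SAP 7.13.3.

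The key secondary endpoint is a proportion in cohorts of about 20 and 10, so one subject matters. The time-to-response analyses have a separate problem: the censoring rule looks for an assessment before a date that itself precedes treatment.

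The SAP does bound other imputed dates. In 9.5.3 and 9.7.4, the end dates of prior remission and of prior therapies are capped at screening. The prohibited-medication date, which feeds a key secondary endpoint, has no bound.

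**Working it through.** The imputation rule has no figure of its own to reproduce. The plan's only sample-size figures do reproduce: 1 − 0.90^20 = 0.878 (stated 88%) and 1 − 0.85^10 = 0.803 (stated 80%). The cohort sizes of 20 and 10 used below are the same ones.

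**Step 1: when the imputed date reaches first dose.** 1 January is never later than a first dose in the same year, and the first of a month is never later than a first dose in the same month. So a year-only date in the year of first dose, or a month-and-year date in the month of first dose, is always imputed on or before first dose.

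**Step 2: worked examples.** The dates are assumed and the visit days come from protocol Table 2, which schedules anti-PLA2R at every visit. First dose is 10-Mar-2021 (study day 1).

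| True start | Recorded | Imputed start | Post-baseline visits that count: true date | Imputed date |
|---|---|---|---|---|
| 20-Sep-2021 (day 195) | year only | 1-Jan-2021 (day −68) | 9 (C1D8 to EOT) | 0 |
| 20-Sep-2021 (day 195) | day missing | 1-Sep-2021 (day 176) | 9 | 9 |
| 29-Mar-2021 (day 20) | day missing | 1-Mar-2021 (day −9) | 2 (C1D8, C1D15) | 0 |
| 15-Feb-2022 (day 343) | year only | 1-Jan-2022 (day 298) | 10 (C1D8 to FUV) | 10 |

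The harm depends on the shared month or year. It is absent in the second and fourth rows.

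**Step 3: how often a partial date would behave this way.** Assume first dose is uniform over the year and the true start is uniform over the stated study days. The chance that the imputed date falls on or before first dose is:

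| Missing part | Starts on days 2–366 | Starts on days 2–169 |
|---|---|---|
| Day and month | 50% | 77% |
| Day only | 4% | 9% |

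These figures are conditional on a prohibited drug started on study with a date that stays partial. The documents do not say how often that happens.

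**Step 4: censoring.** SAP 7.13.5 defines time as end date − start date + 1. With a pre-dose imputed start, the last earlier assessment is at best a screening value. At study day −1 the time is −1 + 1 = 0 days, and at day −42, the earliest screening day, it is −42 + 1 = −41 days. For an imputed start at day −68, before the screening window opens, no assessment exists and the time is undefined. The C1D1 fallback in the same table is for subjects with no post-baseline assessment, and this subject has them.

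**Step 5: effect on BIRR.** One responder lost is 1/20 = 5 points in Cohort 1 or 1/10 = 10 points in Cohort 2. With illustrative counts and Clopper-Pearson intervals:

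- Cohort 1: 14/20 = 70% [45.7, 88.1] becomes 13/20 = 65% [40.8, 84.6].
- Cohort 2: 6/10 = 60% [26.2, 87.8] becomes 5/10 = 50% [18.7, 81.3].

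**Step 6: whether a floor at first dose is enough.** In the first example the floored date is 10-Mar-2021. It still precedes every post-baseline visit, so 0 of 9 count. Suppose instead that the date is bounded by the last visit at which the drug was not recorded, here EOT on day 169. Then the eight visits before EOT count, and EOT counts too if the SAP says that an assessment at the bounding visit is prior to the start.

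**The case against.** The strongest defence is that the rule is a deliberate worst case. It counts against the drug in an uncontrolled trial without hypothesis testing, and SAP 11.1 also takes a worst-case approach to partial adverse-event dates. Cases should also be scarce. Protocol 8.3 requires start dates, protocol 11.1 asks for a reason for missing data, and concomitant medication is recorded at every visit. Protocol 8.8.5 withdraws subjects who start prohibited IST, which makes a year-only date unlikely. SAP 8.3 flags imputed values in listings, and SAP 10.10 repeats BIRR without subjects who received relevant IST, whatever the start date.

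Most of this stands, and it keeps the point small. It does not remove it. A worst case should still be a possible case, and a conservative intention does not supply a censoring time where none exists. The 10.10 analysis drops the subject from numerator and denominator. If only this subject were excluded, the illustrative Cohort 1 result would be 13/19 = 68.4%, neither the 14/20 that the true date gives nor a corrected main BIRR.

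A reader might make two stronger inferences that the documents do not support. One is that every response of the subject is lost. OPR is expressly exempt, and the by-visit table states no cut-off. The other is that the missing floor at first dose is the cause. As Step 6 shows, such a floor removes the impossible date but restores no response. The cause is earliest-date imputation that ignores the visit record.

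**Conclusion.** The point holds as a minor but real gap in SAP 7.13.6. Followed as written, the rule can turn a true responder into a BIR or BPR non-responder and leave the time-to-response censoring zero, negative or undefined. Nothing else in the SAP corrects the main analysis.

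The cost of 5 or 10 points per subject is conditional on four things: a prohibited drug started on study, a start date that stays partial, a month or year shared with first dose, and a qualifying response before the true start. The bias is against the drug. The percentages in Step 3 rest on uniform dates and are not estimates of how often this will occur.

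**What to change.** Amend SAP 7.13.6 and 7.13.5 as follows:

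1. Query every partial start date of a prohibited medication.
2. If the date stays partial, impute the earliest date consistent with all known data. For a start known to be on study, this is not before first dose and not before the last visit at which the drug was not recorded. State that assessments at that visit count as prior.
3. Do not apply this floor to a drug begun before first dose and still ongoing, because it would misdate a true pre-treatment start.
4. Let the documented data review override the imputed date where there is evidence.
5. Report BIRR with the latest consistent date as a sensitivity bound.
6. Censor at C1D1 when no post-baseline assessment precedes the start.

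The cost is a few sentences in the SAP, some programming to find the last visit without the drug, and a little more data review. The information is available because concomitant medication is recorded at each visit in protocol Table 2. The main analysis becomes slightly less of a worst case.

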## 8. STATISTICAL METHODOLOGY

### 8.1. General principles of statistical programming

The statistical analysis will be performed on the analysis study database with appropriate software, SAS Software version 9.4 or above (SAS Institute, Cary, N.C.).

### 8.2. Variable types and descriptive statistics

Descriptive statistics will be calculated using as reference the number of subjects in the relevant analysis population (any exception will be specified) according to the nature of the data as follows:

**Continuous variables** (e.g. age, body weight): number of non-missing observations, number of missing observations, arithmetic mean, standard deviation (StD), minimum and maximum values, quartiles (median, Q1 and Q3).

If there are less than 5 observations, only the number of non-missing observations, arithmetic mean, median, minimum and maximum will be presented.

Descriptive statistics of plasma concentrations and PK parameters will include number of observations, arithmetic mean, geometric mean, StD, median, coefficient of variation CV (%), geometric CV (%), minimum and maximum. Geometric mean and the geometric CV (%) will be derived from non-zero values. For plasma concentrations, the number of non-zero values (m) will also be reported.

**Categorical variables:** (e.g. gender) number of non-missing observations, the number of missing and the relevant percentage on the analysis population, number and relative frequencies.

In case of subcategories, the relative frequencies will be calculated on the basis of the subjects in the respective category, in this case a footnote will be added explaining the different denominators.

**Time variables (durations):** Will be summarized using arithmetic mean, StD, minimum and maximum values, median and quartiles (Q1, Q3) and will be presented in months (unless otherwise stated).

**Time to event variables:** (e.g. Time to Response) Unless otherwise stated, Kaplan Meier estimates of Q1, Median, and Q3 along with their 95% Confidence Intervals will be presented.

The majority of data obtained on the eCRF and entered into the database will be provided in separate data listings showing individual subject values. The planning and reporting of statistical analyses will be carried out as described in the CROs standard operating procedures (SOPs).

### 8.3. Convention on missing data

Unless otherwise specified, missing data will not be imputed. Details on missing data imputation are present in the respective sections.

In all listings, imputed values will be flagged.

#### 8.4. Data included in the analysis and cut-off date

All the analyses will be performed using data collected in the database up to the data cut-off date. A cut-off date will be defined for each of these analyses and will be specified in the outputs.

Any data collected beyond the cut-off date will not be included in the analysis. Only data with an assessment date or event start date prior to or on the cut-off date will be included in the analysis.

All events with an event start date either before or on the cut-off date and an event end date after the cut-off date will be reported as “continuing at the cut-off date”. The same rule will be applied to events starting either before or on the cut-off date and not having a documented end date. This approach applies, in particular, to adverse event and concomitant medication reports. For these events, the end date will not be imputed and therefore will appear as missing in listings.

If it is required to impute an end date to be able to perform a specific analysis, the cut-off date needs to be imputed as an end date. The imputed date will be displayed and flagged in the listings.

Any data collected beyond a subject’s withdrawal of consent will not be included in the analysis; except for SAEs and the date of death provided by a confirmed public registry and subject status entered after the date of withdrawal of consent on e.g. early treatment discontinuation eCRF page.

The data before cut-off for the primary analysis includes all data until the last subject completes Cycle 6 of treatment, i.e. after the EOT visit, or 28 days after the last subject received the last dose of MOR202 for early terminated subjects.

Table 8-1 below indicates the analyses performed for the primary and final analyses.

**Table 8-1 Analysis included in primary and final analysis**

Analysis	Primary Analysis	Final Analysis
Incidence and severity of TEAEs	X	X
Immunological response	X	X
Anti-MOR202 antibodies	X	X
MOR202 serum concentration	X	X
Incidence and severity of AEs in follow-up phase	X	X
CCI	X	X
	X	X
	X	X
	X	X
	X	X
	X	X

#### 8.5. Specifications and analysis database

Based on dataset in SDTM format, analysis datasets adhering to CDISC ADaM standard will be generated with SAS software, version 9.4 or above, after the soft lock of data for the primary completion

analysis or hard lock of complete study database for the final analysis and according to agreed Analysis Dataset specifications (ADS).

### **8.6. Pooling of investigative sites**

Data will be pooled from all investigative sites for the analyses. The justification for this is based on the following:

The sites will follow protocol harmonized across the countries in the sense of study population and outcome measures (in case of country specific protocol amendments).

The sponsor will provide close monitoring of study procedures and compliance for all sites.

Each site is expected to recruit a few subjects only.

The study sites must use unified data collection procedures.

## **9. SUBJECT DISPOSITION, BACKGROUND AND BASELINE CHARACTERISTICS**

### **9.1. Subject disposition - Screened subjects**

The number (%) of subjects who were

Screened

Screen failure

Not treated subjects, i.e. successfully screened but never treated

In the FAS population, i.e. received at least one dose of MOR202

will be summarized and listed by cohort, country, and overall based on SCR. Percentages will be calculated based on the number of subjects screened.

The reason for screen failures (i.e. the violated inclusion or exclusion criteria) will be listed by cohort on SCR.

Subjects who were successfully screened but never started MOR202 treatment will be listed on SCR.

### **9.2. Subject disposition – Treatment and follow-up phase**

The following summaries and listings by cohort and overall will be provided, based on the number of subjects in FAS:

- Number (%) of subjects treated with study drug
- Number (%) of subjects successfully completed treatment phase (without early treatment discontinuation)
- Number (%) of subjects, who discontinued treatment early in the treatment phase
- Reason for early treatment discontinuation
- Number (%) of subjects, who discontinued study early in the treatment phase
- Reason for early study discontinuation in the treatment phase
- Number (%) of subjects entered the follow-up phase

- Number (%) of subjects ongoing in follow-up phase
- Number (%) of subjects completed the follow-up phase (i.e. having their scheduled last visit)
- Number (%) of subjects discontinued study early in the follow-up phase
- Reason for early study discontinuation in the follow-up phase

### 9.3. Protocol deviations

The number (%) of subjects in the FAS with any protocol deviation as well as the protocol deviations will be tabulated by deviation category (as specified in the Protocol deviation specification form) and will be summarized by cohort, overall and by site, and tabulated according to the categories in the Protocol deviation specification form.

Only protocol deviations directly affecting the subject will be reported. Protocol deviations pertaining to the study centers will not be considered.

In a table, for each protocol deviation, the number (%) of events (incidence) and the number (%) of subjects experiencing the protocol deviation will be displayed by cohort and overall on FAS.

A frequency table by visit will be produced for the number (%) of subjects with missed visits in the FAS with the reason for the missed visit (including missed visits in the context of COVID-19).

Protocol deviations will be listed by cohort on FAS.

### 9.4. Demographic characteristics

All summaries will be presented by cohort and overall for the FAS. Listings for demographic data will be produced by cohort on FAS.

The following continuous variables will be summarized by cohort and overall:

- Age at screening (Year of screening – Year of birth, in years)
- Height at screening (cm)
- Weight at screening (kg)
- Body Mass Index (BMI) ( $\frac{kg}{m^2}$ ) at screening, calculated as  $BMI = \frac{Weight (kg)}{Height (m)^2}$
- Body Surface Area (BSA) ( $m^2$ ) at screening, calculated as

$$BSA (m^2) = \sqrt{\frac{Height (cm) \times Weight (kg)}{3600}} \quad (3)$$

The following categorical variables will be summarized by cohort and overall:

Age categorized: 18 – 64 years, 65 – 84 years,  $\geq 85$  years

Gender

Race (White, Black or African American, Asian, American Indian or Alaska Native, Native Hawaiian or other Pacific Islander, or Other)

Female Subjects of child bearing potential: Yes or No

Male Subject Vasectomized: Yes or No

